## Attachments

## Data Collection & Research Materials

In this section, please provide the following:

- Describe all sources or methods for obtaining research materials about or from living individuals (such as specimens, records, surveys, interviews, participant observation, etc.), and explain why this information is needed to conduct the study.
- For each source or method described, please list or attach all data to be collected (such as genetic information, interview scripts, survey tools, data collection forms for existing data, etc.).
- If you will conduct a record or chart review, list the beginning and end dates of the records you will view.

Aim 1: Determine acceptability, composition, and preference of consumption of moringa and placebo in porridge.

Subjects will provide their ratings of taste, texture, visual appearance, palatability.

Aim 2: Test the hypothesis that three months of daily moringa leaf supplementation to breastfeeding mothers will improve infant or to children will improve their own nutritional status via measurements of infant growth, vitamin A, and iron deficiency

Anthropometric Measurements: Weight, height (mothers and children 24 months and older), length (infants and children less than 24 months), head circumference (infants), and mid upper-arm circumference (mothers and children) will be measured by trained study personnel monthly.

Weight: Women will be measured clothed without footwear alone and while holding unclothed infants. Infant weight will be determined by subtracting mother's weight. Children will be measured without clothes except for underwear. The mean of three consecutive measurements will be recorded to the nearest 10g. The scales will be calibrated monthly.

Length/Height: Recumbent length will be measured by a sliding infantometer for infants and children up to 24 months and standing

stadiometer in adult women or children 24 months and older without footwear or headgear. The mean of three consecutive measurements will be recorded to the nearest 0.1cm.

Mid-Upper Arm Circumference (MUAC): MUAC for mothers and children will be measured with a standard WHO-issued tape by measuring midpoint between the relaxed elbow and top part of shoulder then taking a measurement of the circumference of the bent arm at that point. The mean of three consecutive measurements will be recorded to the nearest 0.1 cm.

Head circumference: A standard measuring tape will be extended from the broadest part of forehead to the broadest part of the back of the head for infants. A mean of three consecutive measurements will be recorded to the nearest 0.1cm.

Standardization: For infants and children, weight for age, weight for length/height, and length/height for age will be compared to WHO standard deviation tables or Z scores and assigned their Z score. Wasting is low weight for length/height; stunting is low length/height for age; underweight is low weight for age. These are all measures of undernutrition. Mild undernutrition is defined for any of those parameters as <-1 to and including <-2; moderate undernutrition is <-2 to and including -3; severe undernutrition is <-3. Infants or children with Severe Acute Malnutrition defined as severe wasting (weight or length for height <-3), and/or the presence of nutritional edema will be referred to the nearest nutritional rehabilitation center for treatment as per standard WHO protocol. For mothers, Body Mass Index will be calculated (weight / height squared in metric units) and MUAC recorded.

Quality Control: Participants will be consecutively measured by the same instruments. The study coordinator will perform monthly quality control assessing variance between measurers for all measurements in order to ensure consistent measurement. Retraining and observed measurement will occur for any inconsistencies. Patients who do not arrive for their monthly visits will be contacted to remind them if contact information is available, and then visited at home if unable to come to the health center.

Vitamin A: serum retinol binding protein will survey infant vitamin A levels as an efficient measure of vitamin A at the individual level.

(46,47) Other assays of vitamin A are more informative at the population level. Measurement of the systemic inflammatory marker CRP (C-reactive protein) will allow for assessment of Vitamin A with and without correction for inflammation.

Iron: low hemoglobin is a proxy of childhood iron deficiency utilized internationally by UNICEF in LMIC. Iron levels can be measured via their transporters and intermediate forms. Calculation of a transferrin receptor-ferritin index from ferritin and soluble transferrin receptor will lessen the impact of fluctuations in ferritin from inflammation.(48,49)

**Aim 3: Assess mechanisms of improved infant or child growth and nutritional status as defined by improved infant intestinal health using biomarkers of Environmental Enteric Dysfunction and prevalence of diarrhea**

Sample collection: Baseline and exit visit collection of stool samples, prevalence of diarrhea

Intestinal health measurements: Markers of environmental enteric dysfunction (fecal neopterin, myeloperoxidase, alpha-1- antitrypsin), and prevalence of maternal and infant acute diarrheal illness (>3 watery stools in 24 hours). The rationale for this choice of biomarkers comes from the largest study of markers of environmental enteric dysfunction to date, the MAL-ED cohort, that determined that fecal neopterin, myeloperoxidase, and alpha-1-antitrypsin provide the most sensitive measures of intestinal inflammation and integrity in breastfeeding infants.(50,51) MAL-ED additionally established improved performance of these fecal markers over the previous standard of urine lactulose:mannitol ratio to assess intestinal integrity. These assays will be completed at the UK Biomarker Analysis Laboratory with send-out as needed to UK approved facilities. The impact on intestinal health may also be visible in mothers directly consuming moringa. For this reason, we are collecting maternal stool and analyzing it for the same markers of EED as well as for fecal calprotectin as a measure of intestinal inflammation. In addition to more directly quantifying moringa's impact on intestinal health, increased maternal intestinal integrity may lead to improved nutrition and impact her breastmilk quality or quantity.

**Aim 3: Assess mechanisms of improved infant growth and nutritional status of infants as defined by improved breastmilk volume and composition including Vitamin A precursors and antioxidants.**

Sample collection: At exit, maternal breastmilk.

Breastmilk measurements: Volume (24 hour pre and post-breastfeeding infant weights), vitamin A and its precursors (retinols), antioxidants (catalase, Vitamin E, lactoferrin), and nutritional profile (fatty acid profile and protein analysis). Measures of breastmilk volume include assessment of 24 hour breast pumping or hand expression or weighing the infant before and after feeding for 24 hours.(52–56). Breastmilk contains a wide variety of nutrients necessary for growth and multiple bioactive compounds that can dramatically affect infant health by modifying inflammation. Breastmilk components vary according to time from birth as well as maternal nutritional status, dietary intake, and disease states. Compounds that act to modify inflammation include vitamins and their precursors such as Vitamin A, retinols, and Vitamin E, as well as catalase, lactoferrin, and certain fatty acids.(57–59) All assays will be completed in Eurofin Laboratories. Due to the likelihood of moringa to improve any pre-existing maternal vitamin A or iron deficiency and this, in turn, affecting the composition of breastmilk (most notably in vitamin A precursors), we will also collect maternal blood for vitamin analysis.

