### Data collection:

Monthly anthropometrics for mother, infant, and child. These include infant weight, length and maternal and child weight, height/length, and mid-upper arm circumference.

Enrollment and exit quantitative surveys including but not limited to Food Frequency Questionnaire from which we will calculate Dietary

Diversity Score.

Mother, infant and child finger or finger/ heel stick for hemoglobin and capillary blood collection at study enrollment and exit.

Mother, infant and child feces collection at study enrollment and exit.

Daily recording by parent in provided diary of daily moringa percent consumption, incidence of diarrhea, diagnosis by health professional of medical condition in mother, infant, or child.

Lactating Women:

24 hour volume of breastmilk at study enrollment and exit

Breastmilk sample collection (est. 5ml) at study enrollment and exit

We would like to complete one more anthropometric measurement (weight and length) of enrolled infants in the next few months; this is 8-12 months from study start.

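### The written MUAC procedure finds the midpoint with the elbow relaxed and then tapes a bent arm with no angle, tension rule or named side: a minor measurement error that limits how MUAC values can be described, but does not bias the arm comparison.

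*Combined protocol and SAP*

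**What the plan says.** The Data collection list under Study Design includes monthly "maternal and child weight, height/length, and mid-upper arm circumference". Data Collection & Research Materials repeats that "mid upper-arm circumference (mothers and children) will be measured by trained study personnel monthly". The enrolled young infants have weight, length and head circumference instead.

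The MUAC paragraph has two steps. The site is found "with a standard WHO-issued tape by measuring midpoint between the relaxed elbow and top part of shoulder". The instruction then continues: "then taking a measurement of the circumference of the bent arm at that point". The mean of three consecutive readings is recorded to 0.1 cm.

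Three other statements bear on the point:

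- **Quality control.** The study coordinator performs "monthly quality control assessing variance between measurers for all measurements in order to ensure consistent measurement", with retraining and observed measurement if inconsistencies appear.
- **Reference standards.** For infants and children, "weight for age, weight for length/height, and length/height for age will be compared to WHO standard deviation tables or Z scores". MUAC is not among these indices. For mothers, "Body Mass Index will be calculated (weight / height squared in metric units) and MUAC recorded".
- **Analysis.** The Statistical Analysis Plan analyses outcomes as change from baseline, within and between groups, at an alpha of 0.05. The supplied text does not name MUAC as a primary or secondary outcome.

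**The concern.** The site is located in one arm position and the tape is read in another, and the second position is not defined. Bending the elbow shortens and thickens the biceps, so the circumference depends on how far the arm is bent and how tense it is. Two staff members could each follow the paragraph correctly and record different values on the same arm.

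General measurement practice has the positions the other way round: the midpoint is marked with the elbow bent, and the tape is read with the arm straight and relaxed. The documents do not reproduce that technique. Even without it, the text leaves the measured posture open.

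Two things are at stake. First, absolute MUAC would be a flexed-arm quantity, and a reader told that a WHO-issued tape was used would probably take it for the conventional one. Second, change from baseline is a difference between two visits, so posture variation enters it twice.

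**Working it through.** **1. Inputs.** From the documents: relaxed elbow when the midpoint is found; bent arm when it is taped; three readings averaged to 0.1 cm; a monthly between-measurer check; analysis by change from baseline; alpha 0.05, with sidedness not stated. Arm sizes differ within the protocol: up to 50 per arm under Study Population, and 100 per arm under Study Design. The documents give no MUAC standard deviation, expected difference, bent-arm shift or posture variance. There is therefore no stated figure to reproduce, and every noise figure below is an assumption shown as a range.

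**2. A constant shift.** Let bending add a fixed amount c at every visit. Then (Y1 + c) − (Y0 + c) = Y1 − Y0. The shift vanishes from each participant's change and so from the between-arm difference. A shift proportional to arm size would rescale the difference but not create one. Both statements assume that posture does not differ by arm, and nothing in the documents suggests that it does.

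**3. Varying posture.** Let posture contribute an independent error with SD s at each visit. The variance added to a two-visit change is 2s², so the SD added is s√2. If the posture-free SD of change is D, the inflation factor is f = 1 + 2s²/D². With s assumed between 0 and 0.3 cm and D assumed at 0.5 or 1.0 cm:

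| s (cm) | s√2 (cm) | f at D = 0.5 | f at D = 1.0 |
|---|---|---|---|
| 0 | 0 | 1.00 | 1.00 |
| 0.1 | 0.14 | 1.08 | 1.02 |
| 0.2 | 0.28 | 1.32 | 1.08 |
| 0.3 | 0.42 | 1.72 | 1.18 |

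For the last row, 2 × 0.3² = 0.18; 1 + 0.18/0.25 = 1.72, and 1 + 0.18/1.00 = 1.18.

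**4. What that would do to power.** As an illustration, take a true difference of 0.5 posture-free SDs and a two-sided alpha of 0.05. Power is Φ(0.5·√(n/2)/√f − 1.96).

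| f | 50 per arm | 100 per arm |
|---|---|---|
| 1.00 | 70.5% | 94.2% |
| 1.02 | 69.7% | 93.8% |
| 1.08 | 67.2% | 92.5% |
| 1.18 | 63.4% | 90.2% |
| 1.32 | 58.6% | 86.8% |
| 1.72 | 47.9% | 76.9% |

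The lowest row pairs the largest assumed posture SD with the smallest assumed SD of change. It is the edge of the range, not an expected value.

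**5. What the safeguards reach.** Averaging three consecutive readings reduces reading error within one posture, but leaves a difference in posture between visits untouched. A between-measurer check can expose staff who bend the arm to different degrees. It cannot expose a bent-arm position that all staff share, and it is not designed to show one measurer's drift between visits.

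**6. Where MUAC is used.** WHO Z scores are assigned to three indices, none of them MUAC. Severe acute malnutrition is defined by severe wasting and/or nutritional edema. The inclusion and exclusion criteria do not mention MUAC. Maternal MUAC is recorded with no cut-off.

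**The case against.** The strongest case on the other side is that this is a drafting slip with no analytic consequence. Exchanging the two words for arm position gives a conventional procedure, and the measurers are trained. The data-collection attachments listed in the application were not among the supplied text and may hold the field instruction. The randomised comparison uses change from baseline, so a shared shift drops out. No planned classification uses MUAC. The Statistical Analysis Plan is in the past tense and the one further visit requested covers infant weight and length only, so rewriting the sentence may alter no MUAC value.

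Most of this stands and sets the severity. It does not show that the written procedure is sound. It also leaves open whether reported values came from a bent or a relaxed arm, which a reader of the results would need to know.

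Some stronger readings are tempting but not supported:

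- **Every MUAC value is shifted and noisier.** That requires the sentence to have been followed literally, and the documents give no figure for either effect.
- **Thin mothers and children will be classed as better nourished.** No classification by MUAC is planned.
- **MUAC and BMI are the only maternal nutritional measures.** They are the two maternal anthropometric indices, but the protocol also plans maternal hemoglobin at enrollment and exit, and maternal blood for vitamin analysis.
- **A common wrong position always passes quality control unnoticed, whatever its form.** This is true of a position shared by all staff, but differences in angle between measurers are what the monthly check can detect.

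**Conclusion.** The point holds as a minor measurement-procedure error. As written, the midpoint is found with the elbow relaxed and the circumference is taped on a bent arm of unspecified angle, tension and side. If staff followed the text, maternal and child MUAC is a posture-dependent flexed-arm circumference. Absolute values then cannot be presented as, or compared with, conventional relaxed-arm MUAC, and within-measurer posture variation between visits can add noise to the change from baseline.

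The bias in the randomised change-from-baseline comparison from a constant shift is zero. The loss of precision is not known: 0 to 72% extra variance over the assumed ranges, with zero not excluded. The infant stunting outcome that drives the sample size is untouched, because those infants have no MUAC. The conclusion rests on literal adherence to the sentence, on posture being unrelated to arm, and on MUAC being analysed in the same way as the other outcomes.

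**What to change.** 1. **Correct the sentence.** Mark the midpoint between shoulder and elbow with the elbow bent; tape the circumference at that mark with the arm straight, relaxed and hanging; use the same arm at each visit; keep the mean of three readings to 0.1 cm.
2. **Add arm position to the existing monthly quality check**, so that a posture shared by all staff is looked at directly and not only through variance between measurers.
3. **Confirm from the field instructions and the staff which position was actually used.** If data collection has ended, this is the step that still matters most.
4. **If any values were taken on the bent arm**, flag them in the dataset, say so wherever MUAC is reported, and do not classify them against relaxed-arm references. If the relaxed arm was taped throughout, correct the text and record that it was a wording error.

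The cost is one sentence, a short item in training that already takes place, one query to the site and, if needed, a flag variable. No extra visit, equipment or participant is needed.

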#### Attachments

Attach Type	File Name
DataCollection	Data Collection. Table 1 and 2 Timeline and Outcome measures.docx
DataCollection	Data Collection Tools Moringa BF Kisumu.xlsx

#### Resources

Describe the availability of the resources and adequacy of the facilities that you will use to perform the research. Such resources may include:

- Staffing and personnel, in terms of availability, number, expertise, and experience;
- Computer or other technological resources, mobile or otherwise, required or created during the conduct of the research;
- Psychological, social, or medical services, including equipment needed to protect subjects, medical monitoring, ancillary care, or counseling or social support services that may be required because of research participation;
- Resources for communication with subjects, such as language translation/interpretation services.

This is a single-site project led by [name] with local collaboration from [name] (see below). [name] will supervise

the study via virtual technology and will provide training and monthly quality checks with study personnel. [name] will be on-site in Kisumu and will perform day to day site supervision. Kenya has a long history of research and has developed research infrastructure including in Kisumu. Trained, experienced study coordinators from Kenya will coordinate and perform the study. We will utilize laptops with secure passwords in the field and work computers with secure passwords. Dried blood spots, capillary blood samples, and fecal samples will be transferred to the performing laboratory / storage facility. This will be updated with final logistics once arranged. We will receive ethical approval and guidance from Amref Health in Kenya ESRC. This project is funded through the K01 award from NIH NCCIH/Fogarty International Center to Coinvestigator [name] at the University of California, Davis. From this grant, University of Kentucky will receive a contract to cover lab analyses done at the University of Kentucky. UK will not receive any direct funding or subawards. We have obtained Reliance agreement with UC, Davis. Coinvestigator [name] is a PhD Anthropology Candidate and Executive Director of Pamoja Community Based Organization in Kisumu. Pamoja has worked for decades on improving health outcomes in HIV/AIDS and maternal and child health in the region of our research. [name] and Pamoja will provide cultural and logistical guidance to ensure that our study is culturally sensitive in its approach. Statistical design and analysis is done with the assistance of UK Biostatistician [name].

## Potential Risks & Benefits

### Risks

- Describe any potential risks – including physical, psychological, social, legal, ability to re-identify subjects, or other risks. Assess the seriousness and likelihood of each risk.
- Which risks may affect a subject's willingness to participate in the study?
- Describe likely adverse effects of drugs, biologics, devices or procedures participants may encounter while in the study.
- *Qualitative research* - describe ethical issues that could arise while conducting research in the field and strategies you may use to handle those situations.
- Describe any steps to mitigate these risks.

### Benefits

- Describe potential direct benefits to study participants – including diagnostic or therapeutic, physical, psychological or emotional, learning benefits. This cannot include incentives or payments.
- State if there are no direct benefits.
- Describe potential benefits to society and/or general knowledge to be gained.

Describe why potential benefits are reasonable in relation to potential risks. If applicable, justify why risks to vulnerable subjects are reasonable to potential benefits.

Moringa has been eaten by many cultures around the world for many generations. Moringa leaf is safe to eat. Moringa has been used traditionally to help stop pregnancy; although the true effect on pregnancy is unknown and in the first three months after giving birth, pregnancy is extremely unlikely, moringa will be stopped for any women reporting pregnancy.

It is possible that participants like the taste of moringa porridge or non-moringa (placebo) porridge. It is possible that moringa will cause unreported gastrointestinal side effects such as increased stool frequency due to its high fiber content. Moringa eaten at high amounts can help control high blood sugar. We do not know exactly how much is needed to do that, but we know that it has never been shown to cause low blood sugar. Moringa has been studied with some HIV medicine (nevirapine, an antiretroviral) and does not stop the medicine from working. We do not know if moringa does or does not affect all medications. There is a rare risk that eating moringa can change how well the subject's medicines work for any disease. We will ask subjects' caregivers to collect feces and to wash their hands in soap and water after collection to stay clean. If the caregiver does not wash her or his hands well, there is a risk of oral-fecal transmitted diseases. This is a similar risk to changing diapers.

We will provide practices to maintain confidentiality, however breach of confidentiality is a risk.

We do not know if the subject will experience any benefit from taking part in this study. However, some studies have shown improvement in micronutrient deficiencies when eating moringa every day. The subject will also benefit from receiving flour to make porridge every day for three months even if if moringa is not consumed (placebo). We will not offer money in this study. Although we don't know all the benefits, information learned from this study may help other moms, babies, and children in the future. The risks as described above are minimal and outweighed by the potential current and future benefits.

